Evaluation of pharmacist interventions in lipid management for secondary prevention

NCT06647238

Document date: October 24, 2024

Lipids Research Protocol

Title: Second Time's the Charm: Evaluation of pharmacist interventions in lipid management for secondary prevention

Principal Investigator: [name], BCACP, CDCES, CPP

Co-Investigators:

[name], MSCR

[name], CDCES, BCPS, CPP, DPLA

[name], CDCES, BCPS, CPP

[name], PharmD

[name], BCACP, CDCES, CPP

[name], BCPS, CPP, CDCES

Background/Significance:

Studies have shown prevention of cardiovascular adverse events is directly proportional to percent reduction in LDL.¹ This evidence explains why LDL targets for secondary prevention have continued to be lowered. Cholesterol guidelines have been updated recently and encourage the use of multiple lipid lowering therapies, in addition to statins, for secondary prevention. However, these novel agents can be expensive and difficult to acquire, making prescribing challenging for providers.

This project aims to utilize a pharmacist to evaluate patients for evidence-based therapy and initiate guideline-directed lipid lowering therapy as indicated.

Study Purpose:

The primary objective of this research project is to compare the effect of pharmacist interventions versus usual care in the implementation of guideline directed lipid lowering therapies for secondary prevention.

Study Design: prospective interventional study

Methods/Data Collection

Patient Identification:

- Internal medicine providers and PharmDs will identify patients who are not meeting LDL goals for secondary prevention and could benefit from pharmacist intervention
- SlicerDicer will be utilized to select patients for the control arm as well as potentially for the intervention arm if referrals alone do not meet the sample size goal

Collected data will be stored on a secure Atrium server and de-identified. Data will be analyzed utilizing REDCap. Data collected via EPIC may include:

- Demographic information (age, gender, race)
- Baseline information (recent lipid panel, Lp(a) history)
- Initial hyperlipidemia treatment
- Relevant lab information (renal function, electrolyte values)
- Other co-morbidities (diabetes, CKD, etc)
- Insurance type
- Follow up appointments
- Other relevant patient information for an appropriate hyperlipidemia treatment recommendation

The study period is expected to be 5 months (anticipated November 2024-March 2025).

Inclusion Criteria:

- Age \geq 18 yo

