- Diagnosis of coronary artery disease
- Most recent LDL value > 55
- PCP at 1 of 6 identified clinics

Exclusion Criteria:

- Patients who are no longer an active patient of one of the internal medicine practices
- Patients whose cholesterol is managed by another practice
- Women of childbearing age/potential
- Patients residing in hospice/LTC facilities
- End-stage liver disease

Practice Sites:

- Kannapolis Internal Medicine
- Concord Internal Medicine
- Ardsley Internal Medicine – Harrisburg

- Atrium Health Primary Care Cabarrus Family Medicine – Locust
- Atrium Health Primary Care Cabarrus Family Medicine - Midland

In-person, initial visit:

- Perform medication reconciliation and adherence assessment
- Assess recent laps in EPIC profile
- Educate patient on background of project (pharmacist lipid intervention), provide information sheet, future steps/plans
- Adjust hyperlipidemia treatment, which is part of the routine clinical practice under the collaborative practice agreement.
 - CPP is a licensure that is obtained from the NC Board of Pharmacy and is renewed yearly; CPPs must complete an additional 20 hours of continuing education each year
 - A CPP has an established collaborative practice agreement (CPA) with a supervising physician that outlines the role of the CPP
 - Each pharmacist working on this project either practice as a CPP or are under the direct supervision of CPP
- Order appropriate lab work
- Arrange follow-up with patient regarding medication changes (phone visit)
 - Follow up visits will be scheduled every 6-8 weeks as needed based on patient-specific needs
 - Once LDL<55 (controlled), no further follow up will be scheduled with PharmD
- Will also plan to check Lp(a) for patients who have never had this lab assessed
 - Will provide information sheet on this lab and what to do if it comes back as elevated

Follow up visits:

- Repeat lipid panel prior to appointment, review results
- Assess adherence and access to recommended therapy
- Discuss therapy adjustments
- Set up next follow up visits

The initial in-person visit, or a follow-up telephonic phone visit may be completed by another embedded pharmacist within one of the clinics included in study due to schedule availability. Members of the PharmD team will be trained and follow the protocol during their visits.

Medications are being adjusted as per the usual care services provided by their PCP office and

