PharmD services that are already in place at each practice. Adjustments to medication regimens, comorbidities, and concurrent medications will be made based on national guidelines and evidence-based recommendations that are already allowable by CPP and per our collaborative practice agreement. Any costs/risk associated with medication changes is no additional risk than if they do not participate in the study and would still be subject to these medication changes if they weren't participating in the study. This study and applicable additional intervention are simply offering additional care services provided by a PharmD for closer follow up and offering patients assistance with access to newer therapeutic options.

Control Group:

Patients meeting inclusion criteria will be pulled from SlicerDicer. Any patients previously referred to the project by their provider will be excluded from the control group. Patients included in the report will then be randomized and chosen for retrospective chart review. The goal will be to include 75 patients in both the intervention and control arms. Investigators will perform retrospective chart review for the study period and record the same data as collected for patients in the intervention arm.

Primary endpoint: patients with LDL within goal (<55) (yes/no)

Secondary endpoints:

- Percent LDL reduction (will use baseline LDL and lowest LDL)
- Medication related problems identified and solved
- Medications initiated or titrated
- Number of patients who were provided assistance with access to medication
- Prevalence of elevated Lp(a)

Data and Safety Monitoring:

Principal investigator and co-investigators will meet monthly to re-evaluate patient enrollment and ensure all investigators are adhering to study protocol.

Statistical Analysis:

Data will be analyzed after de-identification using descriptive statistics or inferential statistics as appropriate and will be collected, organized, and stored through REDcap. T-test will be utilized to compare pharmacist intervention versus usual care on the primary outcome. Descriptive statistics will be utilized to report secondary outcomes.

Feasibility of Project:

The anticipated start date for patient enrollment is November 2024. Statistical analysis will be finalized by April 2025. Anticipate presentations/publication in May or June 2025.

Informed Consent:

Participants will be required to provide signed informed consent prior to inclusion in the study.

References:

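### The control exclusion covers only provider-referred patients, so intervention patients found through SlicerDicer, and possibly those identified by PharmDs, can be drawn as controls

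*Combined protocol and SAP*

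**What the plan says.** Patient Identification (under Methods/Data Collection) describes how patients reach the intervention arm. Clinic staff come first: "Internal medicine providers and PharmDs will identify patients who are not meeting LDL goals for secondary prevention and could benefit from pharmacist intervention". SlicerDicer selects the controls, and it may also be used "potentially for the intervention arm if referrals alone do not meet the sample size goal".

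The Control Group section starts from the same tool: "Patients meeting inclusion criteria will be pulled from SlicerDicer". It then applies one exclusion: "Any patients previously referred to the project by their provider will be excluded from the control group". The draw itself is random: "Patients included in the report will then be randomized and chosen for retrospective chart review". The goal is 75 patients per arm, and control charts are reviewed for the study period.

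Both arms share the Inclusion Criteria, among them "Most recent LDL value > 55". The Exclusion Criteria do not mention project enrolment or pharmacist contact. No sentence makes the arms mutually exclusive, and no date is given for the control pull.

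**The concern.** The rule that keeps the arms apart is narrower than the recruitment it has to match. It works through provider referral, while the plan foresees at least one route that is not a referral. Followed literally, it leaves an intervention patient found through SlicerDicer in the list from which controls are sampled.

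Two things are at stake. The primary objective compares pharmacist intervention with usual care, and a control arm containing pharmacist-treated patients does not represent usual care. In addition, a patient counted in both arms contributes one outcome twice, which breaks the independence assumed by the t-test named under Statistical Analysis.

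**Working it through.** **Rule against routes**

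| Route into the intervention arm | Caught by the control exclusion? |
|---|---|
| Identified by an internal medicine provider | Yes, if the referral precedes the pull |
| Identified by a PharmD | Unclear: providers and PharmDs are named separately, and the rule mentions only the provider |
| Selected through SlicerDicer (fallback) | No: the plan contrasts this route with referrals |

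The exclusion also turns on previous referral, with no reference date. If controls were drawn while enrolment was still open, a control referred later would not be caught.

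**Inputs for size**

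From the plan: 75 per arm. The plan gives no derivation of that goal, so there is no sample-size figure to reproduce.

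Assumed, because the plan does not give them: goal rates of 40% (intervention) and 15% (control); two-sided 5% level; m intervention patients left in the list by the rule; a list of N patients. Power is by exact enumeration of the two-sample t-test on the yes/no outcome. It treats the arms as independent, so it does not include the effect of double counting. With no overlap, power is 94.0%.

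**Formulas**

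- Expected overlap = 75 × m / N.
- Chance of at least one overlap = 1 − C(N−m, 75) / C(N, 75).
- Dilution (overlapping patients respond like the intervention arm): control rate = 0.15 + (m/N) × (0.40 − 0.15).
- Inflation (overlapping patients are all non-responders): control rate = 0.15 × (1 − m/N).

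**m = 10, dilution**

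| N | Expected overlap | Chance of at least one | Control rate | Power |
|---|---|---|---|---|
| 300 | 75×10/300 = 2.5 | 95% | 15.8% | 92.1% |
| 500 | 75×10/500 = 1.5 | 81% | 15.5% | 92.9% |
| 1000 | 75×10/1000 = 0.75 | 54% | 15.25% | 93.4% |

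**m = 40, both directions**

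| N | Expected overlap | Dilution: control rate, difference, power | Inflation: control rate, difference, power |
|---|---|---|---|
| 300 | 75×40/300 = 10 | 18.3%, 21.7 points, 84% | 13.0%, 27.0 points, 97% |
| 500 | 75×40/500 = 6 | 17.0%, 23.0 points, 89% | 13.8%, 26.2 points, 96% |
| 1000 | 75×40/1000 = 3 | 16.0%, 24.0 points, 92% | 14.4%, 25.6 points, 95% |

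The assumed true difference is 40 − 15 = 25 points. The higher power in the last column is no benefit, because it comes from a biased difference.

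**Why the direction is open**

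Controls must have a most recent LDL above 55. If the list is pulled before treatment takes effect, overlapping patients go on to respond like the intervention arm, and the effect is diluted. If it is pulled later, intervention patients already at goal fail that criterion, the overlap is mainly non-responders, and the difference is inflated.

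**The case against.** The investigators very probably intend separate arms, and the text can be read more kindly than above. SlicerDicer is only a fallback for the intervention arm. The phrase about referrals alone may sum up the preceding bullet, in which case PharmD identification counts as referral. The project pharmacists are clinical pharmacist practitioners or work under one, so provider might include them. If the list is pulled after enrolment closes, previous referral covers every referral made. With a small m the loss of power is slight.

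Most of this stands as a limit on the point. The PharmD gap is an ambiguity, and the timing gap is possible but not shown. The SlicerDicer gap remains: on the plan's own contrast those patients are not referrals, and the rule fails exactly when the fallback is used. Intention does not settle it, since whoever draws the sample will follow the written rule. Signed consent would identify enrolled patients, but no step checks consent or enrolment records against the control list.

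A reader might infer that overlap will certainly occur, or that it must raise the control rate and hide a benefit. The documents support neither. They permit overlap without showing it, and the LDL criterion can turn the bias the other way.

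**Conclusion.** The point holds as a gap in a stated rule. Intervention patients selected through SlicerDicer are not excluded from the control draw, and those identified by PharmDs may not be. Treated patients can therefore enter the usual-care arm, or one patient can appear in both.

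Under the assumed rates, the effect ranges from slight (at m = 10, a power loss of 94.0 − 92.1 = 1.9 points at most under dilution) to material (at m = 40 and N = 300, a loss of about 10 points under dilution, or a difference inflated by 2 points if overlapping patients are all non-responders). The documents give neither m nor N, and m = 40 would mean that more than half of the 75 intervention patients came by uncovered routes. Even at m = 10, at least one overlap is more likely than not across the list sizes shown. The correction should be made because it is cheap and protects the primary comparison. A reader who concludes that the rule fails for every non-referral route, or that the trial will be biased towards no effect, goes further than the text allows.

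**What to change.** Keep the exclusion of referred patients and extend it. Suggested text for the Control Group section:

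> Any patient referred to, identified for, approached for or enrolled in the intervention arm by any route (provider, PharmD or SlicerDicer) during the study period is excluded from the control group. The control list is matched to the intervention log before de-identification, after intervention enrolment closes, and any excluded patient is replaced by the next in the random order.

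Also state the date on which control eligibility (LDL > 55) is assessed.

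The wording should not be limited to enrolled patients. Signed consent is required, so that would return patients who were referred but declined or never attended to the control pool, from which the present rule keeps them out.

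With this text, overlap is zero by construction and the goal of 75 per arm is unchanged. The cost is two sentences, one stated date and one record match. The control sampling frame becomes slightly smaller, and final control selection waits until intervention enrolment closes, which fits the planned retrospective chart review.

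### The protocol does not say when, by whom or as of what date the exclusions apply to controls, so they can be decided on post-entry events or with the study-period LDL in view

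*Combined protocol and SAP*

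**What the plan says.** The Control Group section sets out the sequence for controls. The report step is "Patients meeting inclusion criteria will be pulled from SlicerDicer". Then "Any patients previously referred to the project by their provider will be excluded from the control group". Then "Patients included in the report will then be randomized and chosen for retrospective chart review". Finally, "Investigators will perform retrospective chart review for the study period and record the same data as collected for patients in the intervention arm". The goal is 75 patients per arm, and the primary endpoint is LDL below 55, yes or no.

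The Exclusion Criteria section stands apart from that sequence and carries no reference date. Three of its entries matter here:

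- "Patients whose cholesterol is managed by another practice"
- "Patients who are no longer an active patient of one of the internal medicine practices"
- "Patients residing in hospice/LTC facilities"

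For the intervention arm, the Informed Consent section requires signed consent before inclusion, and care starts at an in-person initial visit.

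On staffing, the visit section says "Each pharmacist working on this project either practice as a CPP or are under the direct supervision of CPP". The chart readers are called only investigators. Of the seven listed on the first page, six show a CPP or PharmD credential. No masking, eligibility lock, exclusion log or replacement rule appears anywhere.

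**The concern.** The two arms can be screened from different vantage points. An intervention patient is accepted before follow-up begins. For a control, the only described step at which anyone opens the chart is a look back over the whole study period, and that look also shows the endpoint.

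Two kinds of exclusion are exposed:

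- **Judgement.** Whether another practice manages the cholesterol of a patient with coronary disease has no operational definition. A reader who already sees the LDL can be swayed by it without any bad faith.
- **Timing.** A control may leave the practice, enter long-term care or have lipid care taken over during the window. Read retrospectively and without a date, the criterion then appears to be met. An intervention patient with the same later event was already in the study.

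If exclusions are applied this way, control membership depends on what happened after entry. Adjustment for baseline covariates does not repair selection on later events or on the outcome itself. The comparison at risk is the primary one.

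**Working it through.** **What the text fixes and leaves open**

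| Step | Intervention arm | Control arm |
|---|---|---|
| Inclusion criteria | Referral, or report if needed | Report |
| Exclusion list | Not dated; inclusion follows consent | Not dated; step, reader and source not stated |
| Chart opened | Initial visit, before outcome | Retrospective review covering the outcome period |
| Later events | Handling not stated | Handling not stated |

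The documents give no goal rates, exclusion rates or power assumptions, so there is no figure of the plan's own to reproduce. Every rate below is an assumption, used only to see which way and how far the control rate could move.

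**1. Exclusion tied to later events.** Let the control goal rate be 20%. If a share s of controls with goal rate g is dropped, the rate among the rest is (0.20 − s·g)/(1 − s). The expected rate is the same whether the places are left empty or filled by charts screened the same way.

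- Lipid care moved elsewhere, s = 5% to 15%, g = 40% to 60%: from (0.20 − 0.02)/0.95 = 18.9% down to (0.20 − 0.09)/0.85 = 12.9%. The control rate falls by 1.1 to 7.1 points.
- Left the practice or entered long-term care, s = 5% to 10%, g = 0% to 5%: from (0.20 − 0.0025)/0.95 = 20.8% up to 0.20/0.90 = 22.2%. It rises by 0.8 to 2.2 points.
- Both together, at the extremes of those ranges: (0.20 − 0.09 − 0.0025)/(1 − 0.15 − 0.05) = 13.4%, or (0.20 − 0.02 − 0)/(1 − 0.05 − 0.10) = 21.2%. The net shift runs from −6.6 to +1.2 points, so its sign is not settled even inside one set of assumptions.

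**2. Exclusion tied to the outcome.** Let e1 and e0 be the fractions excluded among at-goal and not-at-goal controls. The observed rate is q = p(1 − e1)/[p(1 − e1) + (1 − p)(1 − e0)]. Take p = 20%, 75 per arm and no true effect. The false-positive rate is for a two-sided 5% pooled two-proportion test (normal approximation).

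| e1 | e0 | Observed control rate | Shift | False-positive rate |
|---|---|---|---|---|
| 10% | 10% | 0.18/0.90 = 20.0% | 0 | 5.0% |
| 30% | 10% | 0.14/0.86 = 16.3% | −3.7 points | about 9% |
| 10% | 30% | 0.18/0.74 = 24.3% | +4.3 points | about 10% |

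The first row is also what results if eligibility is settled without reference to the outcome. The second favours the pharmacist service and the third counts against it.

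**The case against.** The strongest reply is that the protocol describes selection as finished before any chart is opened. The report is run, referred patients are removed, and the remainder are chosen at random. The stated purpose of the review is to record data. The one exclusion named for controls, prior referral, does not depend on outcome. LDL is an objective laboratory value, so measurement is not exposed.

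Much of this stands, and it limits what can be said. A reader might infer any of the following, and the documents support none of them:

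- **Charts are accepted or rejected during the review, and rejected ones replaced.** No such step is described. The figure of 75 is a goal without a replacement rule.
- **The readers are the pharmacists who deliver the intervention.** The credentials make overlap likely, but it is not stated, and the visit section lets other embedded pharmacists see patients.
- **The effect will be inflated.** An example that strikes out 3 to 5 of an assumed 15 at-goal controls, and none of the other 60, rejects 20% to 33% of successes against 0% of failures and so assumes its conclusion. If 3 of the 15 and 12 of the 60 go, the rate is 12/60 and stays at 20%. Nothing in the documents says that patients whose lipid care moves do better.
- **Later events are handled differently by arm.** The protocol is silent for both.

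What the reply does not answer is where the exclusions are applied to controls. If nowhere, the arms have different eligibility. If from the charts, the only described reading is retrospective and unmasked. An objective LDL does not help, because the exposure lies in who is counted.

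**Conclusion.** The point holds as an unspecified procedure that permits selection on post-entry events or on the outcome, with no safeguard against either. It is more than a missing detail: applying undated exclusions during a look back would make control membership depend on the follow-up period, while intervention membership is set beforehand.

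It does not show that bias will occur, or in which direction. The shifts of −7.1 to +2.2 points rest wholly on an assumed 20% control goal rate and assumed shares and goal rates among those dropped. Exclusions unrelated to outcome give no shift. That is enough to justify settling the procedure before control charts are reviewed, but not to claim an inflated effect.

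**What to change.** Add to the Control Group section:

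1. **Index date.** Define one for all controls, for example the start of the study period, and take the baseline LDL used for inclusion as of that date.
2. **Eligibility.** Fix the random order of the report list and work down it. Judge every exclusion only from entries dated on or before the index date, record each ruling and its reason, and lock the list at 75.
3. **Outcome.** Only after the lock, extract study-period LDL for the locked list by a single report, using the same rule as for the intervention arm.
4. **Both arms.** State that exclusions are judged at entry, and that no one is removed from the primary analysis for a later event (leaving the practice, hospice or long-term care, lipid care moving elsewhere).
5. **Reporting.** Give the number of charts passed over, by reason.

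Where feasible, make the eligibility rulings at the start of the period, before outcome LDLs exist. Telling the same readers to disregard later entries is not full masking. If the rulings must come later, a reader without access to post-index LDL is the better choice, though that may need another person.

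The cost is a few sentences and an earlier screening step, with no added patients. The downside is that a few controls with later events stay in, so slightly more may lack a follow-up LDL.

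### The yes/no LDL endpoint has no rule for patients without a follow-up LDL, and only the pharmacist arm has repeat panels specified, so unequal measurement can bias the primary comparison

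*Combined protocol and SAP*

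**What the plan says.** All references are to the combined protocol and SAP.

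- **Inclusion Criteria:** entry requires "Most recent LDL value > 55", so every patient starts off goal.
- **Primary endpoint:** "patients with LDL within goal (<55) (yes/no". No assessment time, window, choice among several LDL values, or rule for a patient with no new value is given.
- **In-person, initial visit** and **Follow up visits** (pharmacist arm): "Follow up visits will be scheduled every 6-8 weeks as needed based on patient-specific needs". Each visit carries the step "Repeat lipid panel prior to appointment, review results". Pharmacist follow-up then stops on success: "Once LDL<55 (controlled), no further follow up will be scheduled with PharmD".
- **Control Group:** patients who meet the inclusion criteria are drawn at random from an electronic record report. Investigators then review their charts retrospectively and are to "record the same data as collected for patients in the intervention arm". No LDL is scheduled for them, and having one in the period is not a condition of selection. The target is 75 per arm.
- **Statistical Analysis:** a t-test on the primary outcome. Missing data are not mentioned.
- **Methods/Data Collection:** the whole study period is expected to be 5 months, November 2024 to March 2025.

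**The concern.** Recording the same items from both sets of charts governs what is abstracted. It does not cause an LDL to be measured. A control has a follow-up LDL only if usual care ordered one, whereas the pharmacist arm has panels built into its visits.

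Because everyone starts above 55, a patient with no new LDL can be handled in two obvious ways. Carrying the entry value forward makes the patient an automatic no. Leaving the patient out keeps only those who were retested. The plan chooses neither, and neither is reliably unbiased when the arms are measured at different rates. At stake is whether a difference in the primary endpoint reflects lipid control or merely how often LDL was checked. If the choice is left until the charts have been read, it can also be influenced by the result.

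**Working it through.** **The plan's own figure.** The only design figure is 75 per arm. It comes without alpha, power, expected rates or dropout, so it cannot be reproduced. It is used below as given, with a two-sided 0.05 level assumed.

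**1. Missing scored as no, with no true effect.** Assumed inputs: g, the proportion truly at goal, equal in both arms; m, the proportion with a follow-up LDL in each arm, unrelated to the LDL itself.

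The observed rate in an arm is g × m. For example, with g = 25%, 0.25 × 0.95 = 23.75% against 0.25 × 0.50 = 12.5%, a spurious difference of 11.25 points.

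The planned test is t = (p1 − p2) / √(2s²/75), with s² = 75[p1(1 − p1) + p2(1 − p2)]/148 on 148 degrees of freedom. Summing the binomial probabilities of every pair of counts (0–75 in each arm) for which the test rejects gives:

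| True goal rate | Measured, pharmacist vs control | Observed rates | False rejection |
|---|---|---|---|
| 25% | 95% vs 40% | 23.75% vs 10.0% | 63% |
| 25% | 95% vs 50% | 23.75% vs 12.5% | 44% |
| 25% | 95% vs 60% | 23.75% vs 15.0% | 28% |
| 25% | 95% vs 70% | 23.75% vs 17.5% | 16% |
| 25% | 95% vs 80% | 23.75% vs 20.0% | 8.5% |
| 25% | 80% vs 60% | 20.0% vs 15.0% | 13% |
| 25% | 80% vs 70% | 20.0% vs 17.5% | 7% |
| 15% | 80% vs 60% | 12.0% vs 9.0% | 9% |
| 15% | 80% vs 70% | 12.0% vs 10.5% | 6% |
| 10% | 95% vs 40% | 9.5% vs 4.0% | 27% |
| 10% | 95% vs 70% | 9.5% vs 7.0% | 9% |
| 25% | all measured | 25% vs 25% | 4.9% |

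In the 95% versus 40–70% rows, nearly all false rejections favour the pharmacist arm. With equal measurement the t-test on 0/1 data holds its level at about 5%, so the choice of test does not drive the result.

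**2. Measured patients only.** If retesting is unrelated to LDL, this is unbiased but costs power. For 10% versus 30% at goal, power falls from 87% with all 75 per arm to 67% at 90% versus 50% measured.

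If retesting is selective, the control rate shifts. Take a true control rate of 20%:

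- 40% of at-goal and 60% of off-goal controls retested: 0.20 × 0.40 / (0.20 × 0.40 + 0.80 × 0.60) = 14%.
- The reverse: 0.20 × 0.60 / (0.20 × 0.60 + 0.80 × 0.40) = 27%.

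The bias can therefore go either way. A therapy change is one plausible reason for retesting. Suppose 30% of controls have a change (85% retested, 45% at goal) and 70% do not (35% retested, 10% at goal). The observed rate is (0.30 × 0.85 × 0.45 + 0.70 × 0.35 × 0.10) / (0.30 × 0.85 + 0.70 × 0.35) = 0.139/0.50 = 27.9%. The true rate is 0.30 × 0.45 + 0.70 × 0.10 = 20.5%. About 38 of the 75 controls remain.

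**3. What the data alone could support.** Suppose 20% of measured patients are at goal in both arms, with 90% versus 50% measured. Counting missing values at their extremes, the difference runs from 0.18 − (0.10 + 0.50) = −42 points to (0.18 + 0.10) − 0.10 = +18 points.

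**The case against.** The strongest reply is that the plan is silent rather than wrong. A reader might infer that following it as written must give a biased primary comparison. The documents do not support that: the plan neither scores missing values as no nor drops them, and dropping them is unbiased if retesting is unrelated to LDL. This part of the reply stands.

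A reader might also infer that the missing values fall almost entirely on controls. That is too strong. Pharmacist visits are as needed, and the 5-month period includes enrolment, so a patient who joins late may have no repeat panel inside it. The imbalance is likely because panels are specified in one arm only, but its size is unknown. The lower rows of the table show that it could be modest.

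Finally, a documented LDL below 55 during the period, otherwise not achieved, can be a legitimate service outcome if it is declared in advance and labelled as such. That is fair, but it would mix measurement with lipid control, and the plan does not declare it. Nor do the documents make imputation or weighting the only acceptable primary method.

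None of this removes the gap. The endpoint has no value for an unmeasured patient, and the two arms are measured by different processes.

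**Conclusion.** The concern holds as a risk of bias built into the design and left without a rule. It is not a demonstrated bias of known size. Only the pharmacist arm has repeat panels specified, controls rely on usual care, and a patient without a new LDL has no defined outcome. Scoring such patients as no favours the pharmacist arm whenever controls are measured less often. Restricting to measured patients can err in either direction.

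Under missing scored as no, the false-rejection rate runs from 6% to 63% over the assumptions tabulated. It is close to nominal when measurement is nearly equal and far above it when half the controls or fewer are measured. Every goal and measurement rate is assumed, and nothing in the plan secures near-equal measurement. Because this can affect the primary result and costs little to settle, it should be resolved before control charts are abstracted.

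**What to change.** Under Primary endpoint and Statistical Analysis:

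1. Define an index date for both arms, including controls, who currently have none; a common assessment window; and which LDL in that window counts. Apply the same rule in both arms. This matters separately from missing values, because repeated panels with follow-up ending at the first value below 55 give more chances to record a success. Imputation or weighting would not remove that advantage.
2. State that no LDL in the window is missing, not a no.
3. Report the number and percentage with a follow-up LDL by arm.
4. Pre-specify the primary handling of missing values. Multiple imputation or inverse-probability-of-measurement weighting are examples, using arm, baseline LDL, baseline lipid therapy, therapy changes and clinic. Clinic is known from eligibility but must be added to the data list.
5. Show sensitivity analyses with missing scored as not at goal, with measured patients only, and with best- and worst-case bounds. Limit the conclusion if they disagree.

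The cost is protocol wording and a little more analysis work, with no new patients or tests. The confidence interval will be wider if many controls are unmeasured. Imputation or weighting rests on a missing-at-random assumption that the data cannot verify, so the sensitivity analyses must probe it.
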